Exploratory Research Goal: A more exploratory research goal, not considered part of the primary endpoint, would be to define if there are differences in IFN scores between clinical 'responders' and 'non-responders' as defined by changes in IGA, DLQI, or skin-specific scores as defined in Specific Aim 3 below. It is difficult at this point to estimate how many responders versus non-responders there will be in the study, and hopefully, all participants will see clinical improvement, in which case this exercise will not be necessary. Assuming that half of the participants will see clinical improvement as defined by IGA for example (i.e. 20 responders versus 20 non-responders), we are powered to see an effect size of 0.66 between the two groups.

Secondary Endpoint: Change in levels of circulating cytokines.

Endpoint Definition: Statistically significant reduction in the cytokine score at 16 weeks of treatment as defined by two-sided, paired Student's t-test.

Method: To determine the impact of Tofacitinib treatment on the Cytokine Score values (a composite Z score derived from the measurements of IP10, TNF- α , CRP, and IL6), a two-sided, paired Student's t-test will be used to compare baseline and 16 weeks of treatment for participants with good compliance with the study drug (2 or fewer missed pills) and without a confounding reported adverse event in the 7 days prior to the Visit 7 endpoint. With 40 participants, we have 80% power to detect an effect size of 0.45 with a p-value less than 0.05, as calculated by G*Power software.

Exploratory Research Goals: For an exploratory component of this analysis to test the impact of Tofacitinib on individual plasma cytokine levels (15+ cytokines measured in total, see *Research Strategy*), using a non-parametric Kolmogorov-Smirnoff (KS) test with 40 participants comparing baseline and 16 weeks of treatment, we have 80% power to detect an effect size of 0.47 with a p-value <0.05, as calculated by G*Power software, using FDR correction for multiple testing on 15 cytokines. This investigation will include cytokines isolated from both the blood and non-invasive skin tapes. For the exploratory goal of defining differences between responders and non-responders, assuming that half of the participants will see clinical improvement, we are powered to see an effect size of 0.66 for the composite Cytokine Score and 0.68 for individual cytokines.

Tertiary Endpoint: Change in levels of neurotoxic metabolites in the kynurene pathway.

Endpoint Definition: Statistically significant reduction in one or more of three kynurenone dysregulation values at 16 weeks of treatment as defined by a two-sided, paired Student's t-test with FDR correction.

Method: To determine the impact of Tofacitinib treatment on the levels of kynurenone, quinolinic acid, and the kynurenone/tryptophan ratio, a two-sided, paired Student's t-test will be used to compare baseline and 16 weeks of treatment for participants with good compliance with the study drug (2 or fewer missed pills) and without a confounding reported adverse event in the 7 days prior to the Visit 7 endpoint. With 40 participants, we have 80% power to detect an effect size of 0.45 with a p-value less than 0.05, as calculated by G*Power software, and using FDR correction for multiple testing on three KYN pathway dysregulation values.

Exploratory Research Goal: For the exploratory goal of identifying differences between clinical responders and non-responders, assuming that half of the participants will see clinical improvement (i.e. 20 responders versus 20 non-responders), we are powered to see an effect size of 0.66 between the two groups, as calculated by G*Power software.

Tertiary Endpoint: Change in levels of autoantibodies associated with AITD and celiac disease.

Endpoint Definition: Statistically significant reduction in levels of one or more autoantibodies at 16 weeks as defined by a two-sided, paired Student's t-test.

Method: To determine the impact of Tofacitinib on levels of autoantibodies associated with 1) AITD, i.e. anti-thyroperoxidase (TPO), anti-thyroglobulin (TG), and anti-thyroid stimulating hormone receptor (TSHr), and 2) celiac disease, i.e. anti-tissue transglutaminase (TG) and deamidated gliadin peptide (DGP), a two-sided Student's t-test will be used to compare baseline and 16 weeks of treatment. With 40 participants, we have 80% power to detect an effect size of 0.45 with an FDR corrected p-value less than 0.05, as calculated by G*Power software.

Specific Aim 3. To define the impact of JAK inhibition on immune skin conditions in Down syndrome.

Secondary Endpoint: Change in IGA, DLQI, and/or disease-specific scores.

Endpoint Definition: A statistically significant *percentage reduction* in one or more metrics of skin pathology, including: a) IGA values, b) DLQI values, and/or c) disease-specific scores between baseline and 16 weeks as defined by a two-sided, paired Student's t-test.

Method: The first endpoint for this Specific Aim will be to monitor changes in the Investigator's Global Assessment (IGA), which is a well-established, disease-agnostic measurement of skin disease severity that employs a continuous visual analog scale and has good test-retest reliability. A second disease-agnostic secondary endpoint will be the Dermatology Life Quality Index (DLQI), a patient-reported outcome that is commonly used in dermatology trials. The third secondary endpoint for this study is a percentage reduction in the disease-specific measurements used to monitor each skin condition. We will employ Eczema Area and Severity Index (EASI) for AD, Severity of Alopecia Tool (SALT) for AA, Modified Sartorius Score (MSS) for HS, Psoriasis Area and Severity Index (PASI) for psoriasis, and Vitiligo Extent Tensity Index (VETI) for vitiligo. By focusing on a *percentage reduction* in disease-specific scores, we will be able to compare values from participants with different conditions. In every case (IGA, DLQI or disease-specific scores) we will define whether the percentage reduction reaches significance using a two-sided, paired Student's t-test comparing baseline and 16 weeks of treatment. In every case, for 40 individuals, we have 80% power to detect an effect size of 0.45 with a p-value less than 0.05, as calculated by G*Power software. Finally, although we will be analyzing changes between baseline and 16 weeks, data will be also gathered at the intermediate time point of eight weeks for research purposes.

Specific Aim 4. To characterize the impact of JAK inhibition on cognition and quality of life in Down syndrome.

Tertiary Endpoint: Change in any one or more of the cognitive assessments performed.

Endpoint Definition: a statistically significant improvement in any one of the cognitive measures employed between baseline and 16 weeks as defined by a Wilcoxon signed-rank test with FDR correction or a two-sided, paired Student's t-test, as appropriate.

Method: This Aim includes exploratory tertiary endpoints to determine the impact of Tofacitinib treatment on cognitive outcomes in people with DS using cognitive assessments and their subdomains. For example, for Leiter 3 subdomains, we will employ a Wilcoxon signed-rank test (matched pairs) with which we have 80% power to detect an effect size of 0.32 with an FDR-corrected p-value less than 0.05, as calculated by G*Power software. For CANTAB subdomains, we will employ two-sided, paired Student's t-test comparing baseline and 16 weeks of treatment, we have 80% power to detect an effect size of 0.45 with an FDR-corrected p-value less than 0.05, as calculated by G*Power software.

Tertiary Endpoint: Change in PROMIS surveys of quality of life.

Endpoint Definition: A statistically significant improvement in any one or more of the NIH PROMIS tools employed between baseline and 16 weeks as defined by a two-sided, paired Student's t-test.

Method: Efforts in this Aim also include the NIH-developed PROMIS tool for quality of life assessment. Here, we will employ two-sided, paired Student's t-test comparing baseline and 16 weeks of treatment, we have 80% power to detect an effect size of 0.45 with a p-value less than 0.05 as calculated by G*Power software.

Secondary analysis to investigate potential age- and sex-dependent effects.

Although we are unlikely to have sufficient numbers for separate analysis of effects in children versus adults or females versus males, it is possible that the effects of the study drug may differ with age and/or sex, potentially reducing our power to detect significant differences in endpoint measures. To address this issue, we will conduct a series of secondary analyses, which would not affect the definition of the endpoints or the assessment of whether the endpoints were met or not, to investigate potential effects of age and sex as modifiers of the effects of the study drug.

Toward this end, we will use repeated measures ANOVA to test for significant interaction of outcome variables with either age (as a continuous variable) or sex. These analyses will yield p-values and estimates of the difference in effect size per unit of age, or between females and males, for each of the outcome measures. This would allow us to better interpret any potential failure to meet endpoint definitions.

VIII. Summarize Knowledge to be Gained:

The potential knowledge that may be gained from this clinical trial is substantial. The biomedical significance of immune disorders is undisputed – approximately 10% of the American population suffers from an autoimmune disease resulting in hundreds of millions of dollars in medical expenses. Furthermore, individuals with DS are likely the largest human population with a genetic predisposition to autoimmunity and inflammatory disorders, which we hypothesize is due to the consistent activation of the IFN response and consequent widespread immune dysregulation. This clinical trial will, for the first time, evaluate in DS the impact of JAK inhibition on immune skin conditions, on molecular markers of IFN activity and immune dysregulation in DS, and on cognition.

If JAK inhibition proves to be beneficial in any of the endpoints in this trial, this knowledge would have the potential to not only advance the understanding of DS as an immune disorder, but also to advance the mechanistic understanding of the impacts of immune dysregulation in general. Furthermore, the clinical trial will provide a multidimensional analysis of diverse yet intertwined biological processes – immune skin conditions, general immune dysregulation, IFN signaling, and cognition – which has the potential to accelerate the repurposing of JAK inhibitors, or other anti-IFN strategies, for the treatment of a wide range of immune and neurological conditions thought to be driven by IFN signaling. For example, we hypothesize that JAK inhibition could provide therapeutic benefits for diverse autoimmune conditions more prevalent in

DS, pulmonary hypertension, cases of developmental regression, various seizure disorders, and even perhaps be used in combination with anti-amyloid strategies for the treatment of Alzheimer's disease in DS.

IX. References:

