Figure 5. Trisomy 21 induces the kynurenine pathway. **A.** Volcano plot showing results of a plasma metabolomics experiment on 120 participants, 72 of them with T21. **B.** Overview of tryptophan catabolism pathways. **C.** Quinolinic acid (QA) is significantly elevated in plasma of people with DS. **D.** RNA-seq shows that *IDO1* is overexpressed in white blood cells from people with DS. **E.** Spearman correlation analyses revealed strong association between activation of the kynurenine pathway and circulating levels of cytokines such as TNF α measured in the same plasma

neuroinflammatory phenotype of DS (90-98) may have therapeutic benefits, even in adults. Given the well-documented negative impact of hyperactive IFN signaling on brain function, from excessive synapse pruning by IFN-activated microglia to global impairments in cognitive function upon acute IFN α administration (99-106), **we hypothesize that reducing IFN signaling via JAK inhibition could improve cognition and behavior regulation in DS**. Of note, Tofacitinib was shown to cross the blood-brain barrier in mice (107). Thus, we will assess changes in selected cognition and overall quality of life metrics for individuals with DS upon JAK inhibition.

IV. Research Methods

B. Outcome Measure(s):

Name. Evaluate the safety of Tofacitinib in people with DS.

Type. Primary Endpoint.

Time Frame. Baseline through 16 weeks.

Brief Description. Adverse events (AEs) will be recorded, classified, and closely monitored by study coordinators and doctors. Based on published safety data, we calculate that we should have no more than two serious adverse events (SAE) definitely related to treatment over the course of 16-weeks in order to demonstrate comparable safety to the typical population.

Name. Change in IFN scores in the transcriptome of white blood cells.

Type. Primary Endpoint.

Time Frame. Baseline and 16 weeks.

Brief Description. Using published methods, IFN scores will be calculated using RNA-seq from whole blood RNA. A two-sided, paired Student's t-test will be used to determine the significance of any changes observed.

Name. Change in IGA.

Type. Secondary Endpoint.

Time Frame. Baseline and 16 weeks.

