Furthermore, at the end of each study year, the PIs and Clinical Coordination Team will work together to produce an Annual Report. Annual Reports will include (1) a summary of enrollment and retention and participant demographics; (2) a summary of participant adherence to the study protocol; (3) a complete list and overall summary of all AEs; (4) an analysis addressing whether AE rates are consistent with pre-study assumptions; (5) reasons for dropouts from the study; (6) whether all participants met entry criteria; (7) whether continuation of the study is justified on the basis that additional data are needed to accomplish the stated aims of the study; and (8) conditions whereby the study might be terminated prematurely. Annual Reports will not include subject- or group-identifiable material. Each report will only include the Study ID. The Annual Report, and the DSMB report, will also be submitted to COMIRB at the Continuing Review.

Additionally, participants will be notified of UAPs that affect the level of risk of participation, and so result in changes to the protocol or consent, at the time of re-consent for active participants. Participants who have completed active trial participation will be notified in compliance with COMIRB or the NIAMS corrective action plan.

NIAMS will convene a Data Safety and Monitoring Board (DSMB) for this study. DSMB members will have no direct involvement with the study PIs or the investigational agent, Tofacitinib. The DSMB will act in an advisory capacity to NIAMS who monitors participant safety and progress of the study, and review procedures for maintaining data confidentiality, quality, management, and analyses.

Participant Discontinuation and Trial Stopping.

Study doctors, at their discretion, may discontinue Tofacitinib, temporarily or permanently, and/or may remove participants from the study.

Specific trial stopping rules for individual participants are as follows:

- 1) Participant decides to discontinue participation for any reason.

- 2) Participant experiences adverse or allergic reaction to Tofacitinib, as determined by the study doctor.
- 3) Participant experiences an AE that precludes trial completion, as determined by the study doctor.
- 4) Clinically significant abnormal lab finding, as determined by the study doctor. Abnormal lab findings will be repeated within one week to confirm.
- 5) Participant becomes pregnant.

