As described above, our study doctors will monitor AEs and assign a likelihood that they are attributable to Tofacitinib treatment. Published safety data for Tofacitinib for treatment of RA in typical people indicates 9.4 serious adverse event (SAEs)/100 patient years (all SAEs, treatment-related or not) (109). Given that our trial aims to enroll 47 participants for 16 weeks of treatment (though we anticipate up to seven participants would be lost to attrition at various times during the treatment course) for a maximum total of 14.5 patient years of treatment, a comparable number of SAEs is 1.36. Accordingly, and with the knowledge that our population may be more prone to AEs in general without any treatment due to other health conditions, we define the success of our primary endpoint associated with this aim as no more than two SAEs *definitely related* to treatment during the 16-week trial.

For the purposes of ongoing safety monitoring during the optional Extension Arm and after the initially planned 14.5 patient years of treatment time, we will transform this endpoint of "no more than two SAEs definitely related to treatment during the 16-week trial" to an allowable *rate* and apply the same criteria for overall stopping rules. Accordingly, 2 allowable SAEs definitely related to Tofacitinib over the course of 14.5 patient years translates to a rate of 13.83 SAEs/100 patient years (see stopping rules #5 and #6).

Research Methods for Specific Aim 2. To determine the impact of JAK inhibition on the immune dysregulation caused by trisomy 21.

Our results demonstrate that individuals with T21 show obvious signs of immune dysregulation and hyperactivation of IFN signaling at the levels of mRNA signatures, cytokine profiles, and plasma metabolites. In this Specific Aim, we will define whether these inflammatory markers can be driven by Tofacitinib toward values observed in typical people. Importantly, we have already defined the directionality and average

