Method: This number is based on published safety data for Tofacitinib for the treatment of rheumatoid arthritis in the general population, which indicates a rate of 9.4 SAEs per 100 patient years. Given that our trial aims to enroll 47 participants for 16 weeks of treatment (though we anticipate up to seven participants would be lost to attrition at various times during the treatment course) for a maximum total of 14.5 patient years of treatment, a comparable number of SAEs is 1.36.

Specific Aim 2. To determine the impact of JAK inhibition on the immune dysregulation caused by trisomy 21.

The overall goal of our data analysis plan in this Aim is to define which immune processes dysregulated by T21 can be normalized by Tofacitinib treatment, i.e. returned to values observed in typical people. Importantly, data shown in this proposal demonstrate that we have already defined the directionality and average magnitude of the change between people with and without T21. For example, we determined that IFN scores are significantly higher in people with DS (*Figure 3C*) and expect that Tofacitinib will reduce these values. Whereas some of the features dysregulated by T21 may be normalized by Tofacitinib treatment, others may not, and this will provide an important mechanistic insight to understand the molecular underpinnings of immune dysregulation in DS. Accordingly, the endpoints associated with this Specific Aim focus on effects of Tofacitinib (16 weeks of treatment) on four classes of molecular markers of immune dysregulation:

Primary Endpoint: Change in IFN scores in the transcriptome of white blood cells.

Endpoint Definition: Statistically significant reduction in average IFN scores between baseline and 16 weeks as defined by a two-sided, paired Student's t-test.

Method: To determine the impact of Tofacitinib on IFN scores, a two-sided, paired Student's t-test will be used to compare baseline and 16 weeks of treatment for participants with good compliance with the study drug (2 or fewer missed pills) and without a confounding reported adverse event in the 7 days prior to the Visit 7 endpoint. With 40 participants, we have 80% power to detect an effect size of 0.45 with a p-value <0.05, as calculated by G*Power software.

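### At most two definitely related SAEs in about 14.5 patient-years cannot show comparable safety: even zero events would not exclude a doubled SAE rate

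*Combined protocol and SAP*

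**What the plan says.** Under IV. Research Methods, Outcome Measure(s), safety is a primary endpoint. The plan states that "we should have no more than two serious adverse events (SAE) definitely related to treatment over the course of 16-weeks" and gives the purpose as "in order to demonstrate comparable safety to the typical population". Hypothesis 1 in section I is framed the same way: the frequency will be no higher than that reported in typical people.

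Research Methods for Specific Aim 1 and the Data Analysis Plan for Specific Aim 1 give the derivation. The benchmark is 9.4 SAEs per 100 patient-years in rheumatoid arthritis, and the former section says that this figure covers all SAEs whatever their cause. The plan notes that "our trial aims to enroll 47 participants for 16 weeks of treatment", and that "we anticipate up to seven participants would be lost to attrition at various times during the treatment course". It concludes: "for a maximum total of 14.5 patient years of treatment, a comparable number of SAEs is 1.36". Success is then defined as no more than two definitely related SAEs.

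Research Methods for Specific Aim 1 also converts the limit for later monitoring: two events "translates to a rate of 13.83 SAEs/100 patient years". Under Participant Discontinuation and Trial Stopping, that rate applies once at least 14.5 patient-years have accrued; before then, more than two definitely related SAEs stop the trial.

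Neither section gives an interval, margin, confidence level or error rate for this endpoint. The IFN-score primary endpoint, by contrast, has a test and a power statement.

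Separately, Safety and Adverse Event Monitoring plans incidence rates per 100 patient-years and lists published category rates. The Annual Report is to contain "an analysis addressing whether AE rates are consistent with pre-study assumptions".

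**The concern.** A low count in a small exposure is weak evidence that a rate is low. The endpoint compares an observed count with an expected 1.36 and reads a count of two or fewer as evidence that the rates are alike. That reading needs a design in which a materially higher rate would usually fail, or an interval that excludes such a rate. Neither is shown.

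The plan itself says that JAK inhibition may have a different safety profile in people with Down syndrome, and that this population may be more prone to adverse events even without treatment. Enrolment starts at age 12. A primary endpoint could be declared met, with comparable safety claimed, on data that also fit a several-fold excess.

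**Working it through.** **Inputs from the documents.** 47 participants, 16 weeks, benchmark 9.4 SAEs per 100 patient-years (PY), pass if 2 or fewer events, up to 7 lost to attrition.

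**Step 1: reproduce the plan's figures.**
- Exposure: 47 x 16/52 = 14.46 PY (stated as 14.5).
- Expected SAEs: 0.094 x 14.5 = 1.363 (stated as 1.36).
- Rate at two events: 2/14.46 = 13.83 per 100 PY, as stated. The rounded 14.5 would give 13.79.

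All three reproduce.

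**Step 2: probability of meeting the endpoint.** With Poisson mean m = rate x 14.46, P(X <= 2) = exp(-m)(1 + m + m^2/2).

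| Counted SAE rate | m | P(endpoint met) |
|---|---|---|
| 9.4 (benchmark) | 1.359 | 84% |
| 18.8 (2x) | 2.719 | 49% |
| 28.2 (3x) | 4.078 | 23% |
| 37.6 (4x) | 5.438 | 9% |

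Counting participants with at least one SAE instead (binomial, n = 47) gives 50% at 2x.

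**Step 3: what each passing result excludes.** The exact Poisson upper limit for k events is chi-square(q; 2k+2)/(2 x 14.46), with q = 0.975 for the two-sided 95% limit and 0.95 for the one-sided 95% limit.

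| Events | Two-sided 95% upper limit (per 100 PY) | Multiple of 9.4 | One-sided 95% upper limit (per 100 PY) |
|---|---|---|---|
| 0 | 25.5 | 2.7 | 20.7 |
| 1 | 38.5 | 4.1 | 32.8 |
| 2 | 50.0 | 5.3 | 43.5 |

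A doubling is 2 x 9.4 = 18.8. Every limit lies above it, including the one-sided limit for zero events.

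**Step 4: shorter exposure.** If the seven dropouts leave halfway on average (assumed), exposure is (40 x 16 + 7 x 8)/52 = 13.4 PY. If they contribute nothing (assumed), it is 40 x 16/52 = 12.3 PY. The pass probability at 2x rises to 54% and 59%, and the two-sided upper limit for two events rises to 53.9 and 58.7. In a more extreme assumed case of 20 participants (20 x 16/52 = 6.15 PY), two events would be an observed 32.5 per 100 PY and would still meet the endpoint.

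**Step 5: attribution.** Only definitely related SAEs count, but 9.4 is all-cause. Let f be the share of SAEs called definitely related (not in the documents). At 14.5 PY, a doubled all-cause rate passes 84% of the time at f = 0.5 and 97% at f = 0.25. The 49% is the case f = 1 at full planned exposure.

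**Step 6: scale.** To exclude a doubling with one-sided 95% confidence and 80% power when the true rate is 9.4 (an assumed margin and assumed error rates) takes about 104 PY, passing with 12 or fewer SAEs. That is 104/14.46 = 7.2 times the planned exposure.

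**The case against.** The strongest reply is that this is a small, single-arm, open-label, proof-of-concept trial, and that two events is a workable safety trigger overseen by a DSMB. The claim of comparability is made in one outcome description, while the operative definition in the Data Analysis Plan only sets the count. All of that is fair. It supports keeping the count for monitoring and needs no larger trial. It does not rescue the inference, which the outcome description makes explicitly and hypothesis 1 echoes.

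Four stronger readings are tempting, and the documents do not support them:

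- *A doubled overall SAE rate passes 49% of the time.* That is exact only if every SAE is called definitely related and full exposure is reached. Otherwise the pass probability is higher, so 49% is a floor.
- *The limit ignores exposure.* It is anchored to 14.5 PY, and the plan converts it to 13.83 per 100 PY. However, that rate is a stopping rule for use after 14.5 PY. The gap is narrower: the 16-week success count is not rescaled when exposure falls short. The 20-participant case is hypothetical, and the plan already allows stopping if recruitment problems impair evaluation of the endpoints.
- *One zoster case would look like an excess.* At 14.46 PY one event is 6.9 per 100 PY, against a listed zoster rate of 3.9. But rates are calculated for the study as a whole, and adverse events are recorded through the Extension Arm, which runs from week 16 to week 40. If 25 participants complete it (assumed), exposure is 14.46 + 25 x 24/52 = 26.0 PY and one event is 3.85. The Annual Report check also has no pass/fail rule.
- *No interval will be reported.* The documents state none, but the endpoint definition refers to a Data and Safety Monitoring Plan that does not appear under that title in the text reviewed.

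**Conclusion.** The concern holds as an error of inference. The plan's arithmetic is correct, but meeting this endpoint cannot establish comparable safety. At full planned exposure, a counted rate of twice the benchmark passes about half the time, and no passing count excludes a doubling at either a two-sided or a one-sided 95% level. Two events leave rates up to 50.0 per 100 PY (two-sided) or 43.5 (one-sided) compatible with the data, about 5.3 or 4.6 times the benchmark.

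This rests on Poisson counts, the plan's 9.4 rate, and 14.46 PY as the maximum exposure. Attrition and the restriction to definitely related events both make the endpoint easier to meet. Nothing here suggests that the drug is unsafe in this population, or that the existing trigger is wrong as a trigger.

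**What to change.** 1. In the safety outcome description, delete the clause "in order to demonstrate comparable safety to the typical population", and bring hypothesis 1 and the Specific Aim 1 success definition into line with a descriptive endpoint.
2. Report the SAE rate on actual on-drug patient-years with an exact Poisson 95% interval, saying whether it is one- or two-sided. State the conclusion as the rate that is ruled out. Because 9.4 is an all-cause figure, compare it with the all-cause SAE rate and show the definitely related rate alongside.
3. Leave the existing more-than-two rule unchanged as a monitoring trigger, and do not use it as evidence of comparability.
4. As a secondary matter, give exact intervals whenever adverse event category rates are compared with the published rates, using the exposure actually accrued, including the Extension Arm.

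The cost is wording and a few lines of analysis, with no change to sample size, visits or monitoring. The downside is a less favourable safety claim: the trial will describe the SAE rate with wide limits and will not assert comparability.
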